13.2 Sample Size/Accrual Rate

Phase I component considerations.

The study is designed to escalate the dose if the observed toxicity rate at the current dose is ≤ 0.2365 , and de-escalate the dose if the observed toxicity rate at the current dose is ≥ 0.3585 . If the observed toxicity rate is between 0.2365 and 0.3585, additional patients will be treated at the current dose. For cohorts of size 3, the decision boundaries are shown in table below. Two doses levels of Metformin (850 mg and 1500 mg) are evaluated, beginning with the lower dose.

DLT Regulation of Dose Escalation and De-Escalation									
Number of patients treated	3	6	9	12	15	18	21	24	27+1
Escalate*** if number of DLT <=	0	1	2	2	3	4	4	5	6
Treat additional 3 pts on current dose if number of DLT=	1	2	3	3,4	4,5	5,6	5,6,7	6,7,8	7,8,9
Deescalate* if number of DLT >=	2	3	4	5	6	7	8	9	10
Eliminate** if number of DLT >=	3	4	5	7	8	9	10	11	12

* At the lowest dose level, if the recommendation is to de-escalate AND the dose level has not been eliminated from consideration, 3 additional pts will be accrued at the same dose level; otherwise the trial will stop. Last cohort has 4 patients to reach the required sample size of 28.

** Eliminate dose level and all higher doses from further use.

*** At the time of the design change the study escalated to the highest dose and will continue enrolling additional patients at this dose unless de-escalation is recommended.

Phase II component considerations.

A response rate $\geq 60\%$ would be considered effective for patients undergoing metformin plus standard of care, while a response rate $\leq 40\%$ is not considered as effective. The phase II portion of the trial would require at least 28 evaluable patients treated at the MTD. For the purposes of this study, a response will be defined as overall complete response (CR) or overall partial response (PR) (see Table in section 12.1.4.3). Stable disease or progressive disease will be defined as a non-response. The criterion for significance (alpha) has been set at 0.10. The test is 1-tailed, which means that an effect in one direction (improvement) is expected and will be interpreted. Calculation are based on the assumptions of uniform accrual over time. With the proposed sample size of 28 patients the study will have power of 80% to yield a statistically significant result. The treatment strategy (metformin plus standard of care) is considered effective if 17 or more responses are observed among the 28 patients.

Total study sample size.

This study will enroll at least 3 patients at each dose level and at least 28 patients at the MTD level. Participants will continue to be enrolled and monitored for toxicity according to the rules specified above until 28 efficacy evaluable participants have been enrolled to any single dose level. For the purposes of this analysis, a subject is considered evaluable for the primary endpoint after completing at least one dose of Metformin. It is expected that all dose levels will be safe and assuming that even the highest dose level has a DLT rate substantially lower than the target (i.e. $<10\%$), which is what we expect, we will have more than 99% chance of selecting the top dose level at the end of the trial. In this case the total number of patients enrolled would be 31 (3+28). Retrospective clinical studies have not demonstrated an increase in treatment toxicity for patients undergoing cisplatin for HNSCC while taking metformin. It is anticipated that 1-2 patients per month

will be accrued to the study. Depending on the toxicity, this will allow for completion of study within 33-39 months of study initiation.

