13.0 STATISTICAL CONSIDERATIONS

13.1 Study Design/Endpoints

This is a single arm combination Phase I/II trial of Metformin to determine the maximum tolerated dose (MTD) of metformin among 2 dose levels (850mg, 1500mg administered orally, twice daily) and to evaluate the disease response rate at the MTD. Standard of care conventional chemotherapy (cisplatin) will be administered using current clinical protocols. Dose-limiting toxicity will be ascertained using the Common Terminology Criteria for Adverse Events v4.0. The dose-limiting toxicities ascertained for the phase I component will be gastrointestinal toxicity and hypoglycemia requiring dose reduction. The primary outcome for the phase II component will be disease response rate (RECIST criteria) at 8-12 weeks post treatment completion.

The secondary outcomes will be disease free and overall survival. All analysis of secondary studies will be performed post hoc and will not be used to influence clinical decision making during the therapeutic trial.

This study began as a Phase I “3+3”/ Phase II “Simon” design, but was converted into Bayesian Optimal Interval (BOIN) design before completion of the Phase I to provide monitoring of toxicity beyond the Phase I cohort. BOIN design has algorithmic escalation/de-escalation rules easy to implement like a traditional 3+3 design but allows for specification of the target DLT rate, different size cohorts, is more likely to correctly select the MTD and allocate more patients to the MTD and expands consistent toxicity monitoring to the entire cohort. BOIN design with a target DLT rate of 0.3 and cohort size of 3 begins exactly in the same fashion as the “3+3” allowing for the implemented design change in early stages. Calculations were done using R package BOIN.³²

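### The last column of the BOIN table is applied at 28 patients but carries the 27-patient boundaries, so its de-escalate entry of 10 contradicts the 0.3585 cut point in the same section

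*Combined protocol and SAP*

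**What the plan says.** Section 13.1 gives the design basis: "BOIN design with a target DLT rate of 0.3 and cohort size of 3 begins exactly in the same fashion" as the 3+3 design it replaced. Calculations are attributed to the R package BOIN, without settings.

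Section 13.2 states the rule as rates. The study is to "escalate the dose if the observed toxicity rate at the current dose is ≤ 0.2365", and to "de-escalate the dose if the observed toxicity rate at the current dose is ≥ 0.3585". In between, "If the observed toxicity rate is between 0.2365 and 0.3585, additional patients will be treated at the current dose".

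The table in the same section turns these rates into DLT counts for 3, 6, 9, ... 24 patients, then gives a column headed 27+1. The single-asterisk footnote explains that heading: "Last cohort has 4 patients to reach the required sample size of 28". The entries in that column are escalate at 6 or fewer, stay at 7, 8 or 9, de-escalate at 10 or more, and eliminate at 12 or more.

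Elimination is described only by its consequence: "Eliminate dose level and all higher doses from further use". No rate, posterior probability or prior is given for it.

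**The concern.** The looks step from 24 patients to 28, with none at 27. If the last column was worked out for 27 patients and then used at 28, each count corresponds to a slightly lower rate than intended, and an entry close to a cut point can fall on the wrong side of it. The section would then give two answers for the same data. This is the last toxicity look at the dose that carries the 28-patient efficacy result, so the rule there should be unambiguous.

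**Working it through.** **Inputs.** Target DLT rate 0.30 (Section 13.1). Cut points 0.2365 and 0.3585, the looks, and the table entries (Section 13.2). Three settings are not in the documents and are assumed: the BOIN alternatives are 0.6 and 1.4 times the target (0.18 and 0.42); elimination applies when the posterior probability that the DLT rate exceeds 0.30 is above 0.95; the prior is uniform, so the posterior is Beta(1 + y, 1 + n − y).

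**Step 1: reproduce the cut points.**
- Escalation: ln(0.82/0.70) / ln[(0.30 × 0.82)/(0.18 × 0.70)] = 0.2365.
- De-escalation: ln(0.70/0.58) / ln[(0.42 × 0.70)/(0.30 × 0.58)] = 0.3585.

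Both match the text.

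**Step 2: reproduce the table.** Escalate at the largest whole number not above 0.2365n. De-escalate at the smallest whole number not below 0.3585n. Eliminate at the smallest y whose posterior probability exceeds 0.95.

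| n | Escalate ≤ | De-escalate ≥ | Eliminate ≥ | Posterior one below / at the eliminate entry |
|---|---|---|---|---|
| 3 | 0 | 2 | 3 | 0.916 / 0.992 |
| 6 | 1 | 3 | 4 | 0.874 / 0.971 |
| 9 | 2 | 4 | 5 | 0.850 / 0.953 |
| 12 | 2 | 5 | 7 | 0.938 / 0.982 |
| 15 | 3 | 6 | 8 | 0.926 / 0.974 |
| 18 | 4 | 7 | 9 | 0.916 / 0.967 |
| 21 | 4 | 8 | 10 | 0.908 / 0.961 |
| 24 | 5 | 9 | 11 | 0.902 / 0.956 |
| 27 | 6 | 10 | 12 | 0.897 / 0.951 |
| 28 | 6 | 11 | 13 | 0.935 / 0.971 |

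The rows for 3 to 24 agree with the plan in every entry. The plan's last column (6, 10, 12) agrees with the row for 27, not the row for 28.

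**Step 3: the de-escalate entry at 28.** This needs only the stated cut points.
- 0.3585 × 27 = 9.68, so the boundary at 27 is 10 (10/27 = 0.3704).
- 0.3585 × 28 = 10.04, so the boundary at 28 is 11 (11/28 = 0.3929).
- 10/28 = 0.3571 lies between 0.2365 and 0.3585. The text says stay; the table says de-escalate.
- 0.2365 × 28 = 6.62, so escalate at 6 or fewer is unaffected.

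**Step 4: the eliminate entry at 28.** The rate 12/28 = 0.4286 is above 0.3585, so the stated text and the table are compatible there. Under the assumed posterior rule, 12 of 28 gives 0.935 and 13 of 28 gives 0.971, so the entry would be 13. The exact cutoff matters little. With a uniform prior, the columns for 3 to 24 fix it between 0.938 (6 of 12 is not eliminated) and 0.953 (5 of 9 is), and 12 of 28 falls below that whole range.

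**Step 5: how often the conflict would arise.** Ignoring earlier looks, P(exactly 10 of 28) = C(28,10) p^10 (1 − p)^18, which at p = 0.30 is 0.126. To allow for earlier looks, carry the distribution of the DLT count forward cohort by cohort and drop the paths that meet the table's boundary at 3, 6, ... 24. Two readings bracket the answer.

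| True DLT rate | No earlier looks | Only elimination ends accrual at the dose | De-escalation also ends it |
|---|---|---|---|
| 0.10 | 0.0002 | 0.0002 | below 0.0001 |
| 0.30 | 0.126 | 0.099 | 0.023 |

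**The case against.** The strongest reply is that the mismatch is disclosed and harmless. The table is introduced as applying to cohorts of 3, the heading 27+1 shows where the extra patient was added, and the footnote explains why. The difference is one DLT, in the cautious direction. Section 13.2 also ends enrolment once 28 efficacy-evaluable participants are at a single dose level, so a recommendation to stay has little left to govern. At the lowest dose the single-asterisk footnote prescribes three more patients at the same level after a de-escalation signal without elimination, which is the same action as staying.

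Most of this stands, and it keeps the point minor. It does not remove the contradiction. The footnote makes the last cohort four patients, so there is no 27-patient look to which the column could properly apply, and nothing says that the 27-patient boundaries were kept on purpose.

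A reader might go further and infer that the eliminate entry of 12 also contradicts the section. The documents do not support that: the two stated cut points govern only escalation and de-escalation, and no elimination rule is given. A reader might also infer that this look settles whether the dose is accepted as the MTD. Section 13.2 gives no final MTD selection rule, so that cannot be shown either.

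**Conclusion.** The point holds for the stay and de-escalate entries. At 28 patients the text and the table give different answers for exactly 10 DLTs, and this follows from the stated cut points without any assumption. The whole last column matches 27 patients, which suggests that it was not recomputed when one patient was added.

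For elimination, the finding is that the rule is unstated. That the entry would be 13 rather than 12 is an inference resting on a posterior-probability rule with a uniform prior; it is well supported because that rule reproduces every other eliminate entry.

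The practical size is small. At a true DLT rate of 30% the chance of meeting the conflict is about 0.02 to 0.10 once earlier looks are applied (0.126 without them). At 10%, the upper limit of what the plan expects even at its highest dose, it is about 0.0002 or less. Sample size and the efficacy test are unaffected.

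**What to change.** Relabel the last column 28 and reconcile its stay and de-escalate entries with the stated cut points. On those cut points the column reads escalate at 6 or fewer, stay at 7 to 10, de-escalate at 11 or more. If the sponsor means to use the 27-patient boundaries at 28, the text should say so and mark that look as an exception to the 0.3585 rule.

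Add one sentence giving the elimination cutoff and prior, so that 12 or 13 can be confirmed from the document.

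The cost is one table column and one sentence, with no change to the sample size or the efficacy analysis.

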1.0 PROTOCOL SUMMARY AND/OR SCHEMA

Study Title: A phase I/II study of metformin in combination with cisplatin and radiation in head and neck squamous cell carcinoma.

Study Concept: The purpose of this study is to investigate the safety and efficacy of metformin when used in combination with standard of care cisplatin and external beam radiotherapy (EBRT) for patients with stage III/IV squamous cell carcinoma of the oropharynx, larynx, hypopharynx and oral cavity. Metformin is an anti-diabetic medication which has been widely utilized for nearly 2 decades, with a proven safety profile. Utilization of metformin during treatment of head and neck squamous cell carcinoma (HNSCC) has been shown to be associated with improved disease response, disease free survival and overall survival in retrospective studies. In combination with extensive pre-clinical studies, these data support the hypothesis that metformin can improve chemo-EBRT effectiveness in a prospective clinical trial. The proposed study is designed to determine whether metformin utilization in combination with standard of care cisplatin and EBRT demonstrates increased toxicity (phase I) and whether metformin utilization can improve the primary outcome of disease response (phase II) compared to historical controls treated with chemo-EBRT.

Study Design: This is a prospective study involving stage III/IV patients with squamous cell carcinoma of the oropharynx, larynx, hypopharynx and oral cavity. The phase I portion of the study will test 2 doses of metformin which are within the standard range used for management of diabetes mellitus. The goal of this phase I component is to determine whether metformin use is associated with increased systemic and locoregional treatment toxicity. The phase II portion will use the maximum tolerated dose (MTD) from the phase I to evaluate metformin efficacy in a prospective cohort of 20 patients using disease response as the primary outcome measure.

Number of Patients: 45

Primary Endpoint: The primary endpoint for the phase I component will be toxicity. The primary endpoint for the phase II component will be disease response ascertained via imaging following completion of treatment.

Secondary Endpoints: Secondary endpoints for the phase II component will include: progression free survival and overall survival.

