6.0 TREATMENT/INTERVENTION PLAN

6.1 Agent Administration

All patients will receive immediate release metformin in a pill form that allows for it to be crushed and administered via gastrostomy tube if necessary.

Metformin should be taken 60-90 minutes prior to a meal. The first dose of the day should be taken prior to administration of the daily radiation fraction. On days on

which the patient will undergo cisplatin infusion, metformin should be taken at least 90 minutes prior to cisplatin infusion.

The drug will be dispensed to the patient from the institutional pharmacy with appropriate self-administration instructions. The patients will be provided with a drug log and will be asked to provide the drug log on a weekly basis to the treating team in order to ascertain compliance with administration schedule and instructions.

Dose Level	Drug
DL -1	500 mg, PO, BID
DL 1	850 mg, PO, BID
DL 2	1500 mg, PO, BID

Phase I component:

All patients will undergo a 2 week “lead in” period in order to decrease the gastrointestinal toxicity associated with metformin. During this “lead-in” period, all patients will start metformin at the dose of 500mg PO BID. Dose increases to the targeted Dose levels are delineated in detail below. The start of radiation is Day 1.

The following modification is planned for the Phase I component. We will forgo escalation to Dose level 2 and proceed to the Phase II component using Dose level 1. The previous Dose level 2 information has been left in the protocol for the purpose of documentation (12/19/2018).

Dose level 1: 850mg per os (PO) twice daily (BID). All patients will start metformin 14 days (Day -14) (+/-24hr) prior to initiation of radiation at the starting dose of 500mg PO BID (administered prior to breakfast and prior to dinner), 7 days/week. On day -7 (+/-24hr), the dose will be escalated to 850mg PO BID for the first 3 patients enrolled in the phase I component. The dose of 850mg PO BID will then be continued for the entire duration of chemoradiation, administered 7 days/week. If the timing of radiation start is altered following metformin initiation patient may continue on the study as follows.

- If the timing of radiation is moved up (i.e. sooner than planned), the patient may continue the “lead in” phase as described above, and initiate the target Dose level once the “lead in” phase has been completed.

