12.1.7 Response Review

All imaging will be reviewed by a trained head and neck clinical radiologist blinded to study participation, at the completion of the study.

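### The phase II success rule of 17 or more responses in 28 has exact power of 55% at the 60% target, not the stated 80%

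*Combined protocol and SAP*

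**What the plan says.** All the design inputs are in Section 13.2, under the phase II considerations. A response rate of 60% or more counts as effective and 40% or less does not. Response means overall CR or PR, and the test is one-tailed. On the error rates the plan says "The criterion for significance (alpha) has been set at 0.10" and "With the proposed sample size of 28 patients the study will have power of 80% to yield a statistically significant result". The next sentence gives the rule: "The treatment strategy (metformin plus standard of care) is considered effective if 17 or more responses are observed among the 28 patients". The current plan has no phase II interim look and no other success criterion. Section 13.1 records the design history: "This study began as a Phase I “3+3”/ Phase II “Simon” design, but was converted into Bayesian Optimal Interval (BOIN) design".

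Patient numbers differ elsewhere. Section 1.0 describes phase II as carried out "in a prospective cohort of 20 patients using disease response as the primary outcome measure" and gives 45 patients in all. Section 13.2 requires at least 28 evaluable patients at the MTD and reaches a total of 31 (3 + 28) if the top dose level is selected. Section 6.1 says "We will forgo escalation to Dose level 2 and proceed to the Phase II component using Dose level 1".

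**The concern.** With n, both response rates and the cutoff fixed, type I error and power follow by calculation. A cutoff of 17 in 28 is an observed rate of 17/28 = 60.7%, just above the rate the trial is meant to detect. If the true rate is 60%, the expected count is 28 × 0.6 = 16.8, so the rule asks for slightly more than the expected result. That can succeed only a little more than half the time, which does not fit 80% power.

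This is the only decision rule for the phase II primary endpoint. The error at stake is a false negative: the regimen set aside although it performs as hoped. The rule also leaves a gap in interpretation, because some counts would be statistically significant by the stated alpha and not effective by the stated rule.

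**Working it through.** **Inputs (all Section 13.2):** p0 = 0.40, p1 = 0.60, one-sided alpha = 0.10, n = 28, success at 17 or more, stated power 80%.

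**1. Where 28 patients and 80% can come from.** Because p(1 − p) = 0.24 at both rates, the one-sample normal approximation is

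n = (z₀.₉₀ + z₀.₈₀)² × 0.24 / (0.60 − 0.40)² = (1.2816 + 0.8416)² × 0.24 / 0.04 = 27.05, rounded up to 28.

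At n = 28 the standard error is √(0.24/28) = 0.0926. Normal power is Φ(0.20/0.0926 − 1.2816) = 0.810. The critical count is 28 × (0.40 + 1.2816 × 0.0926) = 14.5, a cutoff of 15. So 28 patients and about 80% power reproduce together, but with 15 rather than 17.

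**2. Exact operating characteristics at n = 28.** With X ~ Bin(28, p), type I error is P(X ≥ c | 0.40) and power is P(X ≥ c | 0.60).

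| Cutoff c | Type I error | Power |
|---|---|---|
| 15 | 0.1025 | 0.813 |
| 16 | 0.0499 | 0.695 |
| 17 (plan) | 0.0215 | 0.551 |

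The written rule falls 80.0 − 55.1 = 24.9 percentage points short. Its chance of missing a true 60% regimen is 1 − 0.551 = 0.449. Solving P(X ≥ 17 | p) = 0.80 gives p = 0.664, so the rule has the stated power only if the true rate is about 66%.

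**3. Could a two-stage design rescue 17?** Section 13.1 says phase II began as a Simon design, so this was checked. A futility look can only remove successes. Over all two-stage designs with 28 patients and a final cutoff of 17, the maximum power is therefore 0.551. For p0 = 0.40, p1 = 0.60, alpha ≤ 0.10 and power ≥ 0.80, the smallest maximum sample size is 28: 16 patients, continue at 7 or more, then 12 more, success at 15 or more (alpha 0.0989, power 0.8031). That 28 was carried over from such a design is an inference; the error does not depend on it.

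**4. The result that falls between test and rule.** With 16 responses the exact one-sided p is P(X ≥ 16 | 0.40) = 0.04995, and the one-sided 90% Clopper-Pearson lower bound is 0.433, above 0.40. This is significant at 0.10 but not effective under the rule. If the true rate is 60%, exactly 16 responses occurs with probability 0.144.

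**5. Single-stage designs meeting both targets.** At n = 28 there is none: 15 exceeds alpha slightly and 16 has 69.5% power. The smallest is n = 30 with 16 or more (alpha 0.0971, power 0.8246).

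**The case against.** Four arguments can be made for the plan.

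*The 80% describes the significance test, and 17 is a separate clinical bar.* The power sentence speaks of a significant result and the rule sentence of effectiveness, and 17 is the first count with an observed rate of at least 60%. The wording allows this reading, but the plan never says that two criteria apply. It would not restore the figure either: exact power for significance at 0.10 is 69.5% (16 or more), and the chance of being declared effective at 60% stays 55.1%.

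*17 may come from the 95% interval.* Section 13.5.2 asks for 95% confidence intervals. The two-sided 95% Clopper-Pearson lower limit is 0.372 at 16/28 and 0.406 at 17/28, so 17 is the first count whose interval excludes 40%. This is a plausible origin for the cutoff, and it means the stated alpha and power, rather than the cutoff, could be what needs changing. The plan does not state it as a criterion, and it does not explain the 80%.

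*The rule is conservative.* This stands: type I error is 2.15% against a permitted 10%, so false claims of efficacy are not inflated. The cost falls on power.

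*Changing the cutoff now may be worse than leaving it.* This stands in part. Section 12.1.7 says "All imaging will be reviewed by a trained head and neck clinical radiologist blinded to study participation, at the completion of the study". That blinds the radiologist; it does not show that the study team is unaware of responses. Scans are done at 8-12 weeks in routine care, the principal investigator analyses outcomes, and the Data Review Committee may see response evaluations. A change made without knowledge of response counts may not be achievable, which favours correcting the stated error rates.

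**Conclusion.** The power statement is wrong as written. The phase II rule has exact power of 55.1% at 60% and type I error of 2.15% at 40%, against a stated 80% and 0.10. The result assumes only independent responses with a common rate, exactly 28 patients in the analysis, and the two rates the plan gives. No method tried at n = 28 (normal approximation, exact single-stage or two-stage) joins a cutoff of 17 to 80% power. Because this is the sole criterion for the phase II primary endpoint and the shortfall is about 25 percentage points, it must be corrected before the result is interpreted.

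The patient numbers in Section 1.0 are a separate, smaller inconsistency. The cohort of 20 conflicts with at least 28 in Section 13.2. The total of 45 is unexplained, and the total of 31 assumes selection of a dose level that Section 6.1 forgoes. The 55% figure depends on none of these.

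**What to change.** Name the exact binomial test in Section 13.2 and adopt one consistent set of figures:

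- **Keep 17 of 28** and restate alpha 0.022 and power 0.55. This is a text edit and the safest choice if responses are already known. If 17 is meant as a clinical bar on top of significance, say so and give the same 55%.
- **Use 16 of 28** and restate alpha 0.050 and power 0.695. This is the lowest single-stage cutoff at n = 28 with exact alpha within 0.10.
- **Use 16 of 30** if alpha 0.10 and 80% power are both to be kept (0.0971, 0.8246). It adds 2 evaluable patients, about 1-2 months at the stated 1-2 per month, and changes the 28 in the enrolment stop and the last toxicity cohort (27+1).
- **Use 15 of 28** only if the plan states exact alpha 0.1025, or if the futility look (continue at 7 or more of the first 16) is reinstated before those responses are known (0.0989, 0.803).

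Lowering the cutoff or adding patients in a single-arm trial under way can look data-driven. Any such change should be dated, and the amendment should record who had seen response data at that time. If independence from the data cannot be shown, take the first option.

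In Section 1.0, change the 20-patient cohort to at least 28, and reconcile the total of 45 with Sections 13.2 and 6.1.
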